## 7.2 Statistical Methods

### 7.2.1 Primary Hypothesis:

We hypothesize that apixaban 5 mg twice daily is associated with a significantly lower rate of the primary composite efficacy outcome compared to matched placebo in patients with calf DVT.

**7.2.1.2 Primary Efficacy Analysis:** All patients randomized to receive at least one dose of apixaban 5 mg or matching placebo control will be included in the primary analysis under intention to treat (see analysis sets below). The analysis of the primary composite endpoint will only include events occurring during the 3 months of study medication use.

Frequency of the primary composite efficacy endpoint will be tabulated by treatment arm without regard to the time the event was observed within the 3 month study period. The Cochran-Mantel-Haenszel test will be used to compare the event rates by treatment group. The pooled estimate of the odds ratio will be used as the primary measure of association for the study.

An exploratory analysis will investigate the time to event is defined as the time from randomization to the first occurrence of a primary composite efficacy outcome event. Patients who were lost to follow-up or who withdrew consent before the end of the three month treatment period will be censored at the last day the patient had a complete assessment for study outcomes within the 3 month study period. The incidence curves of VTE events will be plotted using the Kaplan-Meier estimator by treatment group. The difference in the incidences of the primary composite outcome at 3 months between treatment arms will be estimated and tested using a normal approximation of the binomial distribution.

**7.2.1.3 Safety Analysis:** All patients who received at least one dose of study medication will be included in the safety analysis. The analysis of major bleeding and clinically relevant non-major bleeding events will include those events which occurred during the 3 month study period. Major bleeding events observed later will be described separately.

Frequency of major bleeding and clinically relevant non-major bleeding will be tabulated by treatment arm. The incidence of major bleeding and clinically relevant non-major bleeding will be summarized as a combined endpoint and separate endpoints by treatment arm. The difference in the incidences of the combined endpoint at 3 months between treatment arms will be estimated and tested using a normal approximation of the binomial distribution.

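### The exploratory 3-month difference is tested with a binomial approximation that cannot use the plan's own censoring rule and gives no denominator for lost patients

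*Combined protocol and SAP*

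**What the plan says.** All of this is in section 7.2.1.2 (Primary Efficacy Analysis) of the combined protocol and SAP unless stated.

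- **Primary analysis.** Events are "tabulated by treatment arm without regard to the time the event was observed" within the 3 months. "The Cochran-Mantel-Haenszel test will be used to compare the event rates by treatment group", with a pooled odds ratio as the effect measure.
- **Exploratory analysis.** "An exploratory analysis will investigate the time to event is defined as the time from randomization to the first occurrence" of a primary composite event. Patients lost or withdrawing consent "will be censored at the last day the patient had a complete assessment for study outcomes within the 3 month study period".
- **Curves.** "The incidence curves of VTE events will be plotted using the Kaplan-Meier estimator by treatment group".
- **Difference at 3 months.** The next sentence reads: "The difference in the incidences of the primary composite outcome at 3 months between treatment arms will be estimated and tested using a normal approximation". The approximation it names is the binomial one.

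The paragraph does not say whether these incidences are Kaplan-Meier estimates or crude proportions. It names no denominator, no handling of censored patients and no variance.

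Other sections do not settle it. Section 7.3 puts every randomized subject in the primary efficacy analysis unless data use is refused. Section 7.1 raises 121 to 125 per arm for dropout and missing data, which reads as if such patients leave the analysed number. Section 4.4.3 continues follow-up of withdrawn subjects where they are willing.

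**The concern.** The paragraph builds the means to handle incomplete follow-up (a time origin, a censoring rule, an estimator) and then names a test that uses none of them. Two analysts could follow the same text and report different differences: one keeps a patient lost on day 20 as event-free, the other drops that patient.

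The schedule makes this more than a formality. Under section 6.2 the scans fall on days 7, 14 and 90, so a patient lost after day 14 has no further protocol imaging. What is at stake is the one analysis with a stated rule for lost patients, which is therefore the natural check on the primary result.

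**Working it through.** **Inputs.** From section 7.1: placebo 10.0%, apixaban 1.6%, final two-sided alpha 0.0492, power 80%, 121 per arm raised to 125. From section 6.2: final scan on day 90 ± 7. Assumed: loss unrelated to outcome, loss times and event times uniform over 90 days, and all loss rates above 3.2%.

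**1. The plan's own figure.** With mean rate 0.058, n = [1.967·√(2·0.058·0.942) + 0.842·√(0.10·0.90 + 0.016·0.984)]² / 0.084² = 120.96, so 121 per arm, as stated. Implied attrition is 1 − 121/125 = 3.2%.

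**2. The two crude readings.** Let p be the 3-month risk and d the fraction lost. Half of the events among lost patients go unseen.

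- Lost patients kept as event-free: rate = p(1 − d/2).
- Lost patients excluded: rate = p(1 − d/2) / (1 − d + pd/2).

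True difference: 10.0 − 1.6 = 8.4 points.

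- *3.2% loss in both arms.* Kept: 9.84 − 1.57 = 8.27 (−0.13). Excluded: 10.15 − 1.63 = 8.52 (+0.12).
- *10% in both arms.* Kept: 9.50 − 1.52 = 7.98 (−0.42). Excluded: 10.50 − 1.69 = 8.81 (+0.41).
- *15% placebo, 5% apixaban.* Kept: 9.25 − 1.56 = 7.69 (−0.71). Excluded: 10.79 − 1.64 = 9.15 (+0.75).

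The timing of loss moves these. At 3.2%, if patients are lost before any event can be seen, the kept reading loses 8.4 × 0.032 = 0.27 points. If they are lost after all events have been seen, the excluded reading gives 0.10/0.9712 − 0.016/0.9685 = 8.64 points (+0.24). Hence 0.1 to 0.3 points.

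The bias of the kept reading is −(0.10·d_placebo − 0.016·d_apixaban)/2. It is toward zero unless apixaban loss exceeds 0.10/0.016 = 6.25 times placebo loss.

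**3. Comparison with Kaplan-Meier.** Simulation of both arms, 125 each, 3,000 trials per row; mean difference in points (mean standard error):

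| Loss, placebo / apixaban | Kept as event-free | Excluded | Kaplan-Meier, Greenwood |
|---|---|---|---|
| 3.2% / 3.2% | 8.25 (2.85) | 8.50 (2.93) | 8.38 (2.89) |
| 10% / 10% | 7.98 (2.81) | 8.81 (3.10) | 8.40 (2.96) |
| 20% / 20% | 7.52 (2.74) | 9.26 (3.35) | 8.35 (3.04) |
| 15% / 5% | 7.63 (2.78) | 9.07 (3.17) | 8.33 (2.98) |

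With events fixed at days 7, 14 and 90, the last row becomes 7.77, 9.22 and 8.42.

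At 10% equal loss the ratio of difference to standard error is 2.84 in all three columns (7.98/2.81, 8.81/3.10, 8.40/2.96). At 15% / 5% the ratios separate: 2.74, 2.86 and 2.80.

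**4. The final-scan window.** Assume no loss, a 10% placebo rate with 40% of events found at the final scan, and scans spread evenly over days 83 to 97. Before the final scan, 6% have events. Of the remaining 94%, 4/94 = 4.26% are positive at their scan. If event-free patients are censored on their actual scan date, the number at risk on a day is proportional to j, the scan days left: 15 on day 83, 8 on day 90, 1 on day 97. The hazard on that day is 0.0426/j.

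- Read at day 90: Σ1/j for j = 8 to 15 is 0.725, so the risk is 1 − 0.94·exp(−0.0426·0.725) = 8.9%. Simulation gives 8.8%. Both are too low.
- Read at day 97 with the same censoring: Σ1/j for j = 1 to 15 is 3.318. The product of (1 − 0.0426/j) is 0.867, so the risk is 1 − 0.94·0.867 = 18.5%, far too high.
- With nominal visit days, or with patients whose final scan is negative carried to day 97, the estimate is 6% + 4% = 10%.

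**The case against.** The strongest reply is that the sentence on the difference directly follows the Kaplan-Meier sentence, so the incidences may be meant as Kaplan-Meier estimates compared by a normal test. On that reading the estimate is not biased. This stands as a possible reading, but the text says the curves are plotted and names the binomial, whose variance is not that of a Kaplan-Meier estimate.

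A reader might go further and infer three things that the documents do not support.

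- *That the estimate is too low.* This holds only if lost patients count as event-free. If they are excluded, as the attrition wording in section 7.1 suggests, the direction reverses.
- *That its error is too small.* The binomial standard error suits the crude estimator: at 3.2% loss it is 2.85 points against an empirical spread of 2.89. It is below Greenwood only because Greenwood belongs to another estimator, and with equal loss the test hardly changes.
- *That no planned analysis accounts for loss, the primary included.* The Kaplan-Meier curves carry an explicit censoring rule, section 7.3 adds full-analysis and per-protocol sets, and section 4.4.3 limits loss. How the primary test treats a missing outcome is a separate question, and no section says that such patients count as event-free.

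It is also fair to say that the analysis is exploratory and that the effect is small at the implied attrition.

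**Conclusion.** The point holds as a gap between the censoring rule and the named test. The direction of the bias depends on a denominator that the plan does not state: toward zero if lost patients are kept as event-free, away from zero if they are excluded and placebo loss is equal or higher. Its size is about 0.1 to 0.3 points at 3.2% loss and about 0.4 to 0.8 points at 10% equal loss or 15% versus 5%, against 8.4 planned.

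These figures rest on the planned event rates and on loss unrelated to outcome. No dropout rate is stated, so 3.2% is inferred from 121 versus 125 and the higher rates are assumptions. The conclusion concerns an exploratory analysis; the Cochran-Mantel-Haenszel test and 121 per arm are untouched. It is worth acting on because a better method is already half specified in the same paragraph.

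**What to change.** Replace the sentence on the 3-month difference in section 7.2.1.2 with wording to this effect: the risk difference at 3 months is the difference between arms of the Kaplan-Meier estimates, with Greenwood standard errors; scan findings and completed follow-up are assigned to the nominal visit day; this is the sensitivity analysis for incomplete follow-up of the primary result.

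A day-97 horizon is an acceptable alternative, provided that patients with a negative final scan are carried event-free to day 97 and not censored on the scan date. Reading the curve at day 90 on actual dates should be avoided, because it leaves out events found on days 91 to 97.

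The same binomial wording is used for the bleeding and net-benefit differences, where no censoring rule is given. The denominator for those can be stated in the same edit.

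Cost: one SAP sentence, standard software, and the usual assumption of non-informative censoring. No new data and no change to the primary test or sample size. Label: cheap improvement.

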## Study Summary

Title	A Phase IV, Randomized, Double Blind Placebo controlled Study Evaluating the Safety and Efficacy of Apixaban in Subjects with Isolated Calf Vein Thrombosis
Running Title	Golden Calf Trial
Protocol Number	17-009022
Phase	Phase IV
Methodology	Single center, multi-Mayo site randomized, double blind, placebo-controlled, superiority clinical trial.
Overall Study Duration	36 months
Subject Participation Duration	Each individual will be in the study for 3 months
Single or Multi-Site	Single center, multi-Mayo site Trial
Objectives	There are two primary objectives. The first primary objective is to evaluate whether a strategy of active anticoagulation with apixaban is more efficacious than no anticoagulation (i.e., placebo) when monitored with serial ultrasound imaging in the management of patients with isolated calf vein thrombosis (DVT) for the composite endpoint consisting of prevention of thrombus propagation, pulmonary embolism, recurrent venous thromboembolic events, and all cause mortality. The second primary objective, safety, is to assess the combination of major and clinically relevant non-major bleeding for subjects randomized to apixaban vs. placebo control.
Number of Subjects	The number of patients needed is 250, or 125 in each of the two treatment arms.
Diagnosis and Main Inclusion Criteria	Patients will be recruited for study participation if they have a newly diagnosed venous thrombotic event (DVT) limited to the calf veins.
Study Product, Dose, Route, Regimen	Apixaban (10 mg twice daily for 7 days followed by 5 mg twice daily for 3 months) or matching placebo.
Duration of Administration	Total duration of drug administration will be for the duration of study participation 3 months.
Reference therapy	Serial clinical monitoring as is standard of practice with matching placebo. All patients will undergo serial ultrasound imaging at day 7, day 14, and day 90.
Primary Endpoint	Combined endpoint including thrombus propagation, pulmonary embolism, recurrent venous thromboembolism, and all cause mortality over three months.

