The CACTUS trial is the largest and most recent randomized trial to address this question (15). This was a multinational European trial with 23 participating centers from 3 countries. In this trial, 259 subjects with isolated cDVT were randomized to receive either subcutaneous Nadroparin 171 IU/kg/day or placebo for 42 days. The primary endpoints of the trial included cDVT extension, proximal DVT or PE. The primary safety endpoints were a combination of major plus clinically relevant non-major bleeding. Study endpoints were assessed at 42 and 90 days from enrollment. Venous thrombosis extension was assessed by compression ultrasonography at 3 – 7 days and at 42 days. At 90 days, subjects were contacted by telephone follow up. There was no difference in the primary efficacy outcome at 42 days (3% vs. 5%). At 90 days, the composite outcome was 3.3% in patients receiving LMWH compared to 6.6% for matching placebo (absolute risk difference -2.9%; 95% CI -8.7% to 2.8%; p value 0.28). There were 4% bleeding outcomes in subjects receiving LMWH however only one bleeding event was deemed a major bleed (0.8%). The investigators concluded that LMWH treatment for 42 days was not superior to placebo and resulted in excessive bleeding. There are a number of difficulties with this study which deserve notation (9). First, the slow enrollment of this trial implies strong selection bias. With 22 centers enrolling over 6 years, each center would have enrolled less than 2 patients per year. These investigators met only half of their anticipated enrollment of 572 subjects thus substantially reducing their power for identifying a difference between study arms.

Second, the exclusion criteria were likely too extreme. Patients were excluded from participating if they had a prior history of VTE, cancer, thrombocytopenia, chronic kidney disease, obesity/low body weight or NSAID use. Third, the safety endpoint included major bleeding plus clinically relevant non-major bleeding. The investigators concluded that the bleeding rate of 4% offset any benefits of thrombotic risk reduction however the safety outcome included only 1 patient with major bleeding (0.8%) which is a low and very acceptable rate for VTE treatment. If you compare the bleeding rate of 0.8% to the thrombotic rate of 6.6%, this would seem to be a reasonable tradeoff. In summary, the CACTUS trial provides important data however does not convincingly answer this question.

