#### **1.4 Dose Rationale and Risk/Benefits**

The AMPLIFY investigators compared apixaban (10 mg twice daily for 7 days followed by 5 mg twice daily for 6 months) to enoxaparin/warfarin in 5395 patients with acute VTE (10). At the 6 month follow-up, recurrent VTE occurred in 2.3% in the apixaban group compared to 2.7% in the enoxaparin/warfarin group, meeting the criteria for non-inferiority (relative risk 0.84 (95% CI 0.60-1.18; p<0.001). Similar outcomes were noted regardless of whether the initial event was a DVT or PE. Major bleeding occurred in 0.6% of the apixaban compared to 1.8% of the conventional-therapy group. The difference in major bleeding was superior for apixaban (relative risk 0.31 (95% CI, 0.17-0.55; P<0.001). The AMPLIFY-Ext investigators compared continued apixaban (2.5 mg or 5 mg, twice daily) with placebo in 2486 patients who had just completed 6 – 12 months of treatment for an acute VTE (18). Recurrent VTE or death from VTE was significantly lower in those patients assigned to either 2.5 mg (1.7%) or 5 mg (1.7%) twice daily apixaban compared to placebo (8.8%). Major bleeding rates were similarly low for apixaban 2.5 mg (0.2%), apixaban 5 mg (0.1%) and placebo (0.5%). Based on these data from the AMPLIFY trials, apixaban 10 mg twice daily for 7 days followed by 5 mg twice daily will be the dosing prescribed.

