### 3.3 Safety Endpoints

The primary safety endpoints will include the major bleeding and clinically relevant non-major bleeding. This will include any episode of major bleeding including fatal bleeding or any episode of clinically relevant non-major bleeding. The following criteria will be used to confirm and categorize a bleeding episode:

1. **Major bleeding:** Major bleeding is defined as overt bleeding plus a hemoglobin decrease of  $\geq 2$  g/dL or transfusion of  $\geq 2$  units of packed red blood cells, or bleeding at a critical site: intracranial, intraspinal, intraocular, retroperitoneal, pericardial intra-articular, intramuscular with compartment syndrome, or fatal bleeding.
2. **Clinically relevant non-major bleeding:** Clinically relevant non-major bleeding is defined as any overt, actionable sign of hemorrhage meeting at least one of the following criteria: (i) requiring nonsurgical, medical intervention by a healthcare professional, (ii) leading to hospitalization or increased level of care, or (iii) prompting evaluation.
3. **Minor bleeding:** Minor bleeding is defined as overt bleeding that did not meet criteria for major bleeding.

All suspected recurrent VTE, deaths, as well as all episodes of bleeding and vascular events will be evaluated by a central, blinded, independent adjudication committee. Adjudication results will be the basis for the final analyses.

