#### 6.2 Surveillance and Follow up.

Following randomization, subjects will be assigned to either active treatment with apixaban or placebo control for a total of 90 days. Each subject will then undergo follow up ultrasound imaging at 7 days (+/- 2 days), 14 days (+/- 2 days) and 90 days (+/- 7 days). This ultrasound imaging study will focus on venous thrombus propagation into the proximal venous segments. At each follow up, all venous segments of the involved lower extremity will be imaged. This imaging should be performed at a site participating in this research project. Patients will be called at Days 30 & 60 (+/- 7 days) to check their health status, adverse reactions and medication compliance.

Patients will be instructed to report to the clinic immediately if they had any bleeding or symptoms of recurrent deep-vein thrombosis, pulmonary embolism, or both. All suspected episodes of recurrent thrombosis will be investigated with the use of objective tests, according to prespecified diagnostic algorithms. At 3 months (+/- 7 days), patients will return for a routine clinically indicated ultrasound and clinical assessment.

Study Activity	Day 0	Day 7 (± 2 days)	Day 14 (± 2 days)	Day 30 (± 7 days)	Day 60 (± 7 days)	Day 90 (± 7 days)
Informed consent	X					
History	X					
Concurrent meds	X	X	X	X	X	X

Collect data from clinical physical exam (Ht, Wt, BSA, VS)	X					
Collect Lab Values (CBC, creatinine, ALT/AST) a	X a					
Adverse event evaluation		X	X	X	X	X
B-HCG	X b					
Drug dispensing and collection of any unused drug	X					X
Ultrasound c	X	X	X			X
Telephone survey (appendix A)				X	X	

a = Collect data from clinical testing in the last 4 weeks.

b = Women of child bearing potential only. If not done clinically in the last 2 weeks.

c = The baseline ultrasound will be requested and performed by the provider caring for the patient. This will be a clinically indicated study and will not be repeated for study purposes. This US will serve as the baseline imaging study for trial purposes.

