The outcome of net clinical benefit or harm will be assessed as the composite of the primary efficacy outcome or the principal safety outcome up to day 90. The difference in the incidences of the combined endpoint at 3 months between treatment arms will be estimated and tested using a normal approximation of the binomial distribution. All tests will be conducted at the two-sided 0.05 significance level.

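### No interval is named for the combined bleeding difference; the natural reading, a Wald interval, can understate excess bleeding if placebo bleeding is about 1% or lower

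*Combined protocol and SAP*

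**What the plan says.** The Study Summary names two primary objectives and describes the second as follows: "The second primary objective, safety, is to assess the combination of major and clinically relevant non-major bleeding", compared between apixaban and placebo.

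Section 7.2.1.3 sets the population: "All patients who received at least one dose of study medication will be included in the safety analysis". It tabulates bleeding by arm, combined and by component, and then states: "The difference in the incidences of the combined endpoint at 3 months between treatment arms will be estimated and tested using a normal approximation". The section closes with "All tests will be conducted at the two-sided 0.05 significance level".

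For this difference the plan gives no confidence interval, variance form, small-count alternative, margin or expected rate in either arm. The sample size in section 7.1 concerns the efficacy composite only.

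Information on likely bleeding rates is thin:

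- The only combined rate is in section 1.1, from the largest earlier calf DVT trial: "There were 4% bleeding outcomes in subjects receiving LMWH".
- The placebo figures are for major bleeding alone: 0.5% in the apixaban extension trial (section 1.4), and 0 in the placebo arms with an entry in the section 7.1 table.
- Section 3.3 defines clinically relevant non-major bleeding broadly, as "any overt, actionable sign of hemorrhage meeting at least one of the following criteria", and one of those criteria is simply that the bleed led to an evaluation. Section 6.2 adds: "Patients will be instructed to report to the clinic immediately if they had any bleeding".

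**The concern.** The difference between two observed proportions needs no approximation. Saying that it is estimated by a normal approximation therefore makes most sense as a statement about its uncertainty, and the usual form is the Wald interval. At a 4% rate, 125 patients yield 125 x 0.04 = 5 expected bleeds. With counts this small, a trial that happens to see few bleeds gets both a low estimate and a low standard error, so its upper limit falls short. The error runs in the direction that understates harm.

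When the bleeding test is not significant, the upper limit is what tells a reader how much excess bleeding is still compatible with the data. For a safety objective labelled primary, that limit should be reliable and its method fixed before unblinding.

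**Working it through.** **The plan's own figure.** The documents state no bleeding calculation to reproduce. The efficacy sample size does reproduce. With rates of 10% and 1.6%, mean 5.8%, two-sided alpha 0.0492 and 80% power:

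n = [1.9669 x sqrt(2 x 0.058 x 0.942) + 0.8416 x sqrt(0.10 x 0.90 + 0.016 x 0.984)]^2 / 0.084^2 = 120.96, that is 121 per arm, as stated, rounded to 125 in the plan.

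**Inputs for bleeding.** n = 125 per arm (section 7.1); 95% two-sided, so 2.5% nominal miss per tail (section 7.2.1.3); apixaban 4%, an assumption borrowed from the heparin arm cited in section 1.1; placebo 0-4%, an assumption.

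**Formulas.** Let d = pA - pP from the observed proportions.

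- Wald: d ± 1.96 x sqrt[pA(1-pA)/n + pP(1-pP)/n].
- Newcombe: with Wilson limits (lA, uA) and (lP, uP), lower = d - sqrt[(pA-lA)^2 + (uP-pP)^2] and upper = d + sqrt[(uA-pA)^2 + (pP-lP)^2].

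**Single results at 125 per arm.**

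- 2 vs 0 bleeds: d = 0.016. Wald upper = 0.016 + 1.96 x sqrt(0.016 x 0.984/125) = 0.038, or 3.8 points. The Wilson upper limit for 2/125 is 0.0565 and the placebo term is zero, so Newcombe's upper limit is 5.65 points.
- 0 vs 0: Wald is 0 to 0. The Wilson upper limit for 0/125 is 3.84/(125 + 3.84) = 0.030, so Newcombe is -3.0 to +3.0 points. This outcome is rare: 0.6% of trials at 4% vs 0%, and 4.3% at 2% vs 0.5%.

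**Miss rates.** All 126 x 126 outcomes were enumerated, summing the binomial probability of those whose limit excludes the true difference. Apixaban 4%, n = 125:

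| Placebo | Wald upper miss | Newcombe upper miss | Newcombe lower miss |
|---|---|---|---|
| 0% | 12.0% | 0.6% | 0.5% |
| 0.5% | 7.6% | 1.1% | 0.7% |
| 0.75% | 5.8% | 1.5% | 1.3% |
| 1% | 5.0% | 2.1% | 1.0% |
| 2% | 4.0% | 1.6% | 1.8% |
| 3% | 2.6% | 1.9% | 1.4% |
| 4% | 2.2% | 1.9% | 1.9% |

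Simulation of 1,000,000 trials agrees with the Wald column (for example 7.64% at placebo 0.5% and 4.95% at 1%). Using the pooled standard error gives the same upper-tail figures at placebo 0-1%.

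**Why the first row is not stable.** At 4% vs 0% the miss depends on whether 2 vs 0 counts as one. At n = 125 the Wald limit for 2 vs 0 is 3.80 points, below 4, so it does. At n = 118 it is 0.01695 + 1.96 x sqrt(0.01695 x 0.98305/118) = 0.0402, just above 4 points, so it does not. The miss rate is 4.8% at 118, 13.4% at 121, 12.6% at 123 and 12.0% at 125. At placebo 0.25-1% and n = 121 it is 5.5-6.7%.

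**Other apixaban rates** (2-6% in 0.25-point steps, n = 125). Placebo 0-1%, 85 scenarios: Wald upper misses 4.7-17.8%, median 6.5%, with the maximum at a placebo rate of 0%. Placebo 2-4% with apixaban not below placebo, 117 scenarios: 2.2-4.9%, median 3.2%. Over 422 scenarios (apixaban 0.5-8%, placebo 0-4%, apixaban not below placebo) Newcombe's worst tails are 2.5% upper and 2.1% lower.

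**The test.** The pooled z-test rejects in 0.4%, 2.2%, 4.5%, 4.4% and 4.4% of trials at equal rates of 0.5%, 1%, 2%, 3% and 4%. It does not exceed its 5% level.

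**The case against.** The plan promises no interval and does not say Wald. No margin, success rule or stopping rule uses the limit. Bleeding counts will be tabulated by arm, so any reader can compute another interval. All of this stands, and it confines the point to reporting.

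The documents also lean towards placebo rates at which Wald performs acceptably. The definition in section 3.3 and the instruction in section 6.2 would capture minor events on placebo too, and section 5.6 allows aspirin up to 165 mg/day. This stands as well. Even at placebo 1%, overall two-sided coverage is 94.0%, so the defect there is mainly an imbalance between the tails.

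Four stronger readings are tempting, and the documents do not support them:

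- *The upper limit fails in 12% of trials.* That needs a placebo rate near zero and particular arm sizes; seven fewer patients per arm turns 12.0% into 4.8%.
- *In most trials the reader must rely on the interval because the test is not significant.* The test is significant in 31% of trials at 4% vs 1% and 13% at 4% vs 2%, but there Wald misses only 5.0% and 4.0%. At 4% vs 0%, where the miss is largest, the test is significant in 74%.
- *The placebo major-bleeding figures set a floor for the combined rate here.* The 0.5% comes from 12 months of extended treatment after 6-12 months of anticoagulation (section 1.3). It bounds nothing over 3 months in new calf DVT.
- *The normal-approximation test is invalid.* Its rejection rates at equal bleeding rates show otherwise.

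Finally, the choice among better intervals is partly preference, and Newcombe is over-conservative at very low placebo rates (0.6% and 0.5% per tail at 4% vs 0%). That is fair, but it is not a reason to leave the method open.

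**Conclusion.** The point holds as a low-cost improvement that the sponsor could make, not as an error that invalidates an analysis. If the unnamed interval is Wald and apixaban bleeding is 4%, the upper limit falls below the true excess in about 5-8% of trials at placebo 0.5-1% (nominal 2.5%). With placebo near 0% the figure is unstable, about 5-13%. At placebo 2-4% it is close to nominal (4.0-2.2%). With no bleeds at all the interval collapses to zero width.

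The conclusion rests on an inferred method and on assumed rates; the documents do not settle which placebo range applies. The consequence is limited to how much excess bleeding the report says remains possible.

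**What to change.** In section 7.2.1.3, keep the planned test and add one sentence: the difference in the combined bleeding endpoint will be reported with a two-sided 95% Newcombe hybrid-score interval, and statistical significance will be decided by the test. This is a standard software option, with no change to the test, sample size or data collection.

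Two costs should be accepted knowingly:

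- *Wider intervals.* Mean width is 9.3 points against 7.5 for Wald at 4% vs 1%, 10.9 against 9.6 at 4% vs 4%, and 8.7 against 6.7 at 4% vs 0%.
- *Disagreement with the test.* Newcombe can include zero when the test is significant. At 4 vs 0 bleeds, z = 0.032/sqrt(2 x 0.016 x 0.984/125) = 2.02, yet Newcombe's lower limit is -0.4 points: 0.032 - sqrt[(0.032 - 0.0125)^2 + 0.0298^2] = -0.0036. Such disagreement arises in about 5% of trials at 4% vs 1%, 2% at 4% vs 2%, and 18% at 4% vs 0%. Hence the advance statement that the test decides.

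Miettinen-Nurminen is an alternative if agreement with a score test matters more. Its upper-tail misses match Newcombe's at placebo 0, 0.5 and 1%, but its lower limit misses 3.6% at 4% vs 0.5% and 4.1% at 4% vs 1%, which overstates harm.
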